**Table 1. Outcome Data**

Participant	Time 1: Baseline	Time 2: 24-48 hours post baseline/narrative upload	Time 3: 24-48 hrs after Time 2	1- week Post Upload
Patient	1. Quality of Communication(19)* 2. PROMIS-29 Profile:v2.1(29)* 3. PROMIS Psychosocial Illness Impact a)Positive affect (8)* b) Negative affect (8)* 4. Demographics	1. Quality of communication(19)* 2. PROMIS-29 Profile:v2.1 (29)* 3. PROMIS Psychosocial Illness Impact a)Positive affect (8)* b) Negative affect (8)*	1. Quality of communication(19)* 2. PROMIS-29 Profile:v2.1 (29)* 3. PROMIS Psychosocial Illness Impact a)Positive affect (8)* b) Negative affect (8)*	
Nurse				System Usability Scale (10)*
Pt/Nurse				Exit Interviews

\*(n)= number of items in outcome measure

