**Randomization.** Randomization to the narrative intervention or usual care will occur at the patient level. The random allocation sequence will be computer generated using random block sizes, an allocation ratio of 1:1, and stratification by illness group. The project statistician will generate the allocation sequence using SAS software and the allocation sequence will be uploaded for study use into REDCap. Upon study completion, baseline characteristics between intervention and control patients will be compared using independent samples t-tests (continuous measures) and chi-square tests (categorical measures). Though balance is assumed, statistical adjustment will be used in outcome analyses in the event of pre-treatment differences between conditions.

**Data collection.** All survey and demographic data will be captured using electronic surveys through REDCap on password-protected iPads/laptops.

**Demographics.** At baseline, age, gender, race/ethnicity, education in years, income level, religion/spirituality preference, and clinical details to identify co-morbidities and severity of illness will be collected for all participating patients. This demographic detail will allow description of outcome means and standard deviations in key patient subgroups, including groups defined by patient race/ethnicity and specific chronic illnesses of heart disease or end-stage renal disease.

**Measures.** For Aim 1, the primary and secondary outcome measures will be collected at three time points from all patient participants. (Table 1). The purpose of these times periods are to collect the outcome measures consistently for usual care and intervention participants. This is based on knowledge gained during the K99 study regarding time to complete the narrative intervention. In the K99 study, for the narrative intervention, on average it took 24 hours post narrative interview to upload the patient's narrative into the EHR.

**Exit Interviews and Usability Scale.** For Aim 2, the patient and nurse exit interviews and system usability surveys from the nurses will be collected approximately 1-week post intervention. (Table 1).

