Intervention group: Data collection activities for patients include completing demographic and outcomes measures at baseline (enrollment). Then, they will have outcome measures collected immediately after narrative upload into the EHR (approximately 24 hours after narrative is collected), and 24-48 hours post narrative upload into the EHR. For the narrative intervention group, a one-time audio recorded interview (60-90 minutes) with the research team member will occur once baseline measures have been collected. In addition, the intervention participants will participate in a second audio-recorded audio exit interview (30 minutes) and will collect information on acceptability and feasibility of intervention. This interview will be collected in the private location of the patient's hospital room or may be collected and recorded over the telephone if patient has been discharged from the hospital.

Usual care group: Data collection activities for these patients include completing demographic and outcomes measures only at baseline (at enrollment), and again 24-48 hours after enrollment.

*Outcome Measures:* The estimated time for completion of the 64 items on the questionnaires is approximately 30 minutes. The following questionnaires are included as the outcome measures: Quality of Communication (QOC) which consists of 19 items; PROMIS-29 Profile v.2.1 of 29 items each; and PROMIS Psychosocial Illness Impact {Negative and Positive} Short-Form 8a which consist of 16 items.

*Nurses:* Data collection activities for the nurse participants will include completing a 30 minute exit interview via an audio recorded interview. For the usability testing, data collection will include testing of the EHR interface with the bedside nurses and completion of a short questionnaire at the end of the 30 minute exit interview.

Data collection activities for intervention patient participants include:

1. Completing baseline outcomes measures and demographic information, approximately 30 minutes
2. Completing the narrative intervention via a 60-90-minute audio-recorded interview
3. Completing outcome measures after narrative upload
4. Completing outcome measures 24-48 hours after narrative upload
5. Completing an exit interview via a 30-minute audio-recorded interview.

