Data collection activities for the nurse participants will include completing a 30-minute exit interview via an audio-recorded interview. For the usability testing, data collection will include testing of the EHR interface with the bedside nurses and completion of a short questionnaire at the end of the 30-minute exit interview.

The participants will be recruited through the University of Colorado Hospital.

b. *Sources of Materials*

*Qualitative Data.* For this proposed project, data will only be collected by the research team. Materials include audio recordings of interviews, field notes, and correspondence (i.e., memos, emails) with research

Instructions – How to complete the COMIRB protocol template (Social)

CF-184, Effective 4-26-2010

team members. A total of 240 audio-recorded interviews will be collected—80 interviews for the narrative intervention, 80 for the patient exit interviews, 80 for the nurse exit interviews.

**Quantitative Data.** All patients (intervention and usual care group) will complete a questionnaire at baseline, immediately post narrative upload in the EHR, and 24-48 hours post narrative upload. All survey data will be captured using electronic surveys through REDCap on password-protected iPads/laptops. After each participant's baseline data is collected by the professional research assistant, the participant will be randomized to be included in either the narrative intervention or usual care group. This randomization will occur with the randomization computer-generated algorithm. After the participant is randomized, a unique study identifier for all enrolled participants will be created for a de-identified data set.

Steps of de-identification:

1. The research team will assign the patient participant a de-identified code (i.e. P1) after consent is signed. This code will be the identifier throughout the study to link the narrative interview, the REDcap surveys, and the exit interview.
2. The research team will assign the nurse participant a de-identified code (i.e. N1) that corresponds numerically with the patient participant code.
3. For the REDCap survey data:
  - a. When each participant is added to the REDcap database, the research team will add this assigned de-identified code as the participant identifier.
  - b. Since the participant needs to take the survey three times, at the time of adding the de-identified code, the exact number of times they should take the survey will be added.

c. **Potential Risks**

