*Social.* Participants could feel pressured to participate in the proposed project. Thus, the researcher will arrange with the participant a private time with only researcher and participant present, for collection of the interview. Once in this private setting, the PI will remind them that participation is voluntary and that they may withdraw from the project at any time without any penalty or prejudice. At no time will participants be coerced to participate, and the research team members will remind them that they may refuse to participate at any time during the proposed study.

*Confidentiality.* Although there is a rare risk for breach of confidentiality, the research team member will maintain confidentiality of proposed study materials by assigning each participant a unique study ID number and use this unique identifier throughout the entire study. At the signing of the consents, the research team member will assign a unique numerical identifier, for example: Patient participant 1 = P1 and Nurse Participant 1= N1).

Steps of de-identification:

1. The research team will assign the patient participant a de-identified code (i.e. P1) after consent is signed. This code will be the identifier throughout the study to link the narrative interview, the REDcap surveys, and the exit interview.
2. The research team will assign the nurse participant a de-identified code (i.e. N1) that corresponds numerically with the patient participant code.
3. For the REDCap survey data:
  - a. When each participant is added to the REDcap database, the research team will add this assigned de-identified code as the participant identifier.
  - b. Since the participant needs to take the survey three times, at the time of adding the de-identified code, the exact number of times they should take the survey will be added.

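### Section IV.D gives usual-care patients two outcome assessments where the rest of the plan gives every patient three; if it is followed, Time 3 has no controls

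*Combined protocol and SAP*

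**What the plan says.** Five places bear on the number of assessments.

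- **Section IV.D, part a (Human Subjects).** The intervention arm has three: at enrollment, as soon as the narrative has been uploaded, and 24 to 48 hours after that. The next paragraph gives usual care its own schedule: "completing demographic and outcomes measures only at baseline (at enrollment), and again 24-48 hours after enrollment". That is two.
- **Table 1.** One patient row, not split by arm, carries the same instruments at baseline, at "Time 2: 24-48 hours post baseline/narrative upload" and at "Time 3: 24-48 hrs after Time 2".
- **Section IV.C, Measures.** It says that "the primary and secondary outcome measures will be collected at three time points from all patient participants". The stated purpose is to "collect the outcome measures consistently for usual care and intervention participants".
- **Section IV.D, part b (Sources of Materials, Quantitative Data).** "All patients (intervention and usual care group) will complete a questionnaire at baseline, immediately post narrative upload in the EHR", with a third questionnaire 24 to 48 hours after upload.
- **REDCap set-up steps.** These are printed under Sources of Materials and repeated under Protections Against Risk: "Since the participant needs to take the survey three times", and so "the exact number of times they should take the survey will be added" when the code is entered. No exception is made for usual care.

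On analysis, Section IV.F plans linear mixed models fitted by maximum likelihood, with the two groups compared at every time point. Section IV.C bases the sample size on a time-by-treatment interaction.

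**The concern.** The two schedules cannot both be followed. Staff looking up what a usual-care patient does will find only one paragraph written for that arm alone, and it is the outlier.

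If they follow it, the comparison loses its controls at the last assessment. In Section IV.D the intervention arm's second assessment comes right at upload, and the nurse is alerted only once the narrative is uploaded (Section IV.C). By inference, Time 3 is the comparison that bears most on nurse communication, the primary outcome. The plan also wants means and standard deviations over time for the later efficacy trial, and the control values at Time 3 would be missing. A control who was not surveyed then cannot be surveyed afterwards.

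A smaller, related matter is the clock. Part b of Section IV.D times usual-care follow-up from an upload that does not happen in that arm, and the Time 2 label in Table 1 names two starting points separated by a slash.

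**Working it through.** **Inputs.** 80 patients, 40 per arm (Section IV.D, part a); three assessments (Table 1; Section IV.C, Measures; Section IV.D, part b); two for usual care (Section IV.D, part a).

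**1. What is lost if the two-assessment sentence is followed.** Usual-care follow-up at 24 to 48 hours after enrollment can match only Time 2 of Table 1, so Time 3 has 0 controls.

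- Planned assessments: 80 × 3 = 240. Usual care at Time 3: 40.
- Share of all assessments: 40/240 = 16.7%.
- Share of follow-up assessments: 40/160 = 25%.
- Share of usual-care follow-ups: 40/80 = 50%.

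**2. What can no longer be estimated.** With time as three categories there are 2 × 3 = 6 group-by-time cell means. With usual-care Time 3 empty, the design has rank 5. The Time 3 group difference is lost, and with it one of the two interaction degrees of freedom. Assuming one QOC score, eight PROMIS-29 scores and two illness-impact scores, there are 11 outcomes × 2 follow-up times = 22 group comparisons, of which 11 are lost. If time were instead fitted as a straight line, the model would give a Time 3 figure for usual care, but only by extrapolation.

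**3. Whether the power statement settles the count.** The plan states f = .14 with 80 patients and f = .16 after 20% attrition (64 patients). For the within-between interaction F test, λ = f²·N·m/(1 − ρ), with (m − 1) and (N − 2)(m − 1) degrees of freedom and sphericity assumed. The correlation ρ is not stated, so the values below are assumptions.

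| Times m | Assumed ρ | Minimum f, N = 80 | Minimum f, N = 64 |
|---|---|---|---|
| 3 | 0.5 | 0.143 | 0.160 |
| 2 | 0.6 | 0.142 | 0.159 |

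Both rows round to .14 and .16, so the power section is compatible with either count.

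**4. Why no single power loss is quoted.** Hold the effect itself fixed. With equal arms, λ = N·SS/[4(1 − ρ)], where SS is the sum of squared deviations of the between-arm difference from its mean over the times. Take N = 80, assumed ρ = 0.5, and each effect scaled to f = .14 with three times. Then λ = 0.0196 × 80 × 3/0.5 = 9.41 and power is 78%. Dropping Time 3 gives:

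| Arm difference at Times 1, 2, 3 | SS, three times | SS, two times | λ, two times | Power |
|---|---|---|---|---|
| 0, 1, 1 (sustained) | 0.667 | 0.5 | 7.06 | 75% |
| 0, 1, 0.5 (halving) | 0.5 | 0.5 | 9.41 | 86% |
| 0, 0.5, 1 (linear growth) | 0.5 | 0.125 | 2.35 | 33% |

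At assumed ρ = 0.3 the same shapes move power from 63% to 60%, 73% or 25%; at 0.7, from 95% to 92%, 97% or 50%.

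**5. The clock.** Let B be baseline and U the upload.

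| Source | Time 2 | Time 3 |
|---|---|---|
| Section IV.D, intervention arm | U | U + 24 to 48 h |
| Table 1, counted from baseline | B + 24 to 48 h | B + 48 to 96 h |
| Table 1, counted from upload | U + 24 to 48 h | U + 48 to 96 h |

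If U falls 24 to 48 hours after B, the first two rows agree. The third does not: its Time 2 is the window that Section IV.D uses for the last assessment.

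**The case against.** **Most of the text supports three assessments.** Table 1, Measures and Quantitative Data all say so. The order of steps in Sources of Materials points the same way: the baseline survey is taken, then the patient is randomized, while the survey count is entered with a code assigned after consent. On that order the count of three is set before the arm is known. This is strong but not conclusive, because the same section also creates an identifier after randomization. The two REDCap sentences are copied text and count as one source. Nearby text has similar slips: part a gives every patient two interviews, and part b counts 80 narrative interviews although 40 patients receive the intervention. The word 'only' may also just mean questionnaires without interviews, though two occasions are still listed. A reader might infer that the trial will have no controls at Time 3. The documents do not support that; the loss is conditional on the outlying sentence being followed.

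**The clock may be no contradiction.** A reader might infer that the arms have no common time basis. That goes too far. Measures states a common purpose and cites an average of 24 hours from interview to upload in the earlier study, and reading Table 1 from baseline fits the intervention schedule in Section IV.D. What stands is narrower: part b literally times usual care from an upload it does not have, and the slash in Table 1 is ambiguous.

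**Patients without an upload.** Upload needs the patient's approval, and no section says when an intervention patient without one completes Times 2 and 3. A reader might count this as a further error. It is a missing detail, and the documents do not say how often it would occur.

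**Power.** A reader might infer that the sample-size section presupposes three times, or that a definite amount of power is lost. It does not state a number of times, and the loss depends on an effect shape and a correlation that are not given.

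**Conclusion.** The contradiction in the number of usual-care assessments is real, and confidence in it is high. The two-assessment sentence is probably a drafting slip, but it is wrong as written and should be corrected. Its cost, if followed, is 40 of 240 assessments and every Time 3 control. Maximum likelihood uses patients with incomplete data, but it cannot supply a control mean that no patient was scheduled to provide.

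The size rests on 40 patients per arm. Loss of the full interaction also rests on time being fitted as three categories, which the plan does not state. No power figure is part of the conclusion. The clock is a secondary clarification, held with less confidence where it depends on the slash in Table 1.

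**What to change.** Replace the usual-care sentence in Section IV.D, part a, with: *Usual care group: these patients complete demographic and outcome measures at baseline (Time 1) and the outcome measures again at Time 2 and Time 3.*

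In the same edit, reconcile Table 1 with parts a and b of Section IV.D by stating, for each arm, what Times 2 and 3 are counted from and where intervention Time 2 lies relative to upload. The anchor is the sponsor's choice, and each has a drawback. A baseline anchor matches elapsed time between arms, but with windows of 24 to 48 and 48 to 96 hours, an upload later than 48 hours falls after Time 2. An upload anchor keeps follow-up after the narrative is available but lets elapsed time differ from usual care. The timing for intervention patients without an upload can be settled here too.

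The cost is one sentence and some clarifying words. No survey is added beyond Table 1. Relative to the two-assessment sentence alone, it is 40 more 64-item surveys (19 + 29 + 16 items) of about 30 minutes each: 40 × 0.5 h = 20 patient-hours in total.

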## **Adequacy of Protection Against Risks**

### **a. Recruitment and Informed Consent**

The research team members will recruit, through convenience sampling, patients with serious illness. Study participants will be recruited through University of Colorado Hospital. The research team members will meet weekly and as needed with nursing staff at the hospital and provide updates on recruitment needs until recruitment is complete. At the hospital, the research team member will meet with the charge nurse to identify any potential participants based on diagnoses. If any patients are identified, a research team member will deliver a flyer regarding the study to potential patients to obtain verbal consent, taking precautions to notify the potential participant that participation in the study is voluntary and will not affect care. Once verbal consent is obtained, the research team member, will arrange a convenient time to meet with potential patients to review the study protocols and obtain informed consent. At these initial meetings with the participant, the research team member will complete the official screening, describe the study, review the informed consent, and discuss risks/benefits with the participant. If participant volunteers and meets inclusion/exclusion criteria at this meeting, then the research team member and participant will sign the informed consent.

Recruitment will include the use of flyers given to the nursing staff on the hospital units. The research team members will ensure continual availability of flyers for the key recruitment stakeholders. These flyers will include a brief description of the study, inclusion criteria, and multiple avenues for contacting the PI, such as by e-mail or phone. The research team members will also communicate weekly with the nurse managers on each of the hospital units to identify any potential concerns with the recruitment procedures. This weekly presence within the nurse managers and nursing staff will also act as a reminder to nursing staff on the hospital units about the study and updates on the recruitment needs for the study.

The written consent forms will inform patients and nurses about their own participation in study activities, including randomization, participation in the intervention, and data collection and the risks and benefits of participation. Only the research team members will be responsible for screening, consenting, and collecting all the interviews. The study participants will have the opportunity to decline at anytime throughout the study.

### **b. Protections Against Risk**

Prior to any data collection for the study, the Institutional Review Board approval will be obtained from University of Colorado Institutional Review Board (COMIRB).

*Physical.* Participants could become fatigued during the 60-90minutes interview process. In this event, the research team member will encourage rest periods or if necessary reschedule a return visit to complete the interview.

*Psychological.* There is minor/moderate risk for psychological distress due to the sensitive topics as part of illness stories and the psychological, social and spiritual impacts of serious illnesses. If the participant exhibits any verbal or non-verbal distress, the research team member will allow the participant to stop the interview, reschedule for return visit to complete interview, or allow participant to withdraw consent. If moderate distress

is exhibited, the researcher will help refer them for emotional support either through family, friends, or medical practitioners for follow-up related to the participant's distress. A referral list of appropriate services has been compiled and will be kept with the research team member when conducting interviews. If the participant exhibits any verbal or non-verbal distress, the research team member will allow the participant to stop the interview, reschedule for return visit to complete interview, or allow participant to withdraw consent. If moderate distress is exhibited, the research team member will assist in referring participant for emotional support either through family, friends, or medical nurses for follow-up related to the participant's distress. If any moderate or severe distress is noted, this will be reported immediately to the PI for help in determining if the event meets criteria for a reportable serious adverse event (SAE). If a potential SAE occurs related to the study intervention, the IRB will be notified within 24 hours of occurrence and the participant's involvement in the research study will be discontinued. Participants will be able to contact the PI to discuss any concerns or questions at any time during their participation in the study. We anticipate these to be rare events, given the nature of the data collection procedures.

*Social.* Participants could feel pressured to participate in the proposed project. Thus, the researcher will arrange with the participant a private time with only researcher and participant present, for collection of the interview. Once in this private setting, the PI will remind them that participation is voluntary and that they may withdraw from the project at any time without any penalty or prejudice. At no time will participants be coerced to participate, and the research team members will remind them that they may refuse to participate at any time during the proposed study.

*Confidentiality.* Although there is a rare risk for breach of confidentiality, the research team member will maintain confidentiality of proposed study materials by assigning each participant a unique study ID number and use this unique identifier throughout the entire study. At the signing of the consents, the research team member will assign a unique numerical identifier, for example: Patient participant 1 = P1 and Nurse Participant 1= N1).

Steps of de-identification:

1. The research team will assign the patient participant a de-identified code (i.e. P1) after consent is signed. This code will be the identifier throughout the study to link the narrative interview, the REDcap surveys, and the exit interview.
2. The research team will assign the nurse participant a de-identified code (i.e. N1) that corresponds numerically with the patient participant code.
3. For the REDCap survey data:
  - a. When each participant is added to the REDcap database, the research team will add this assigned de-identified code as the participant identifier.
  - b. Since the participant needs to take the survey three times, at the time of adding the de-identified code, the exact number of times they should take the survey will be added.

In addition, immediately after transcription of participant interviews, the research team member will remove any identifiable names of person or place. A hard copy of the master list of these unique identified numbers and the will be kept in a locked cabinet in the PI's office at the University of Colorado, College of Nursing. The master full-length transcripts, the meta-story and all audio files will be kept on the PI's password protected computer and the research assistant's password protected computer only and uploaded to the secure server at University of Colorado. The research team members will review the meta-narrative with the participant on the password-protected computer. During this review, the patient will be allowed to make changes to the meta-narrative prior to uploading the meta-narrative into the electronic health record. If additional changes are required, these changes will be completed in person with the participant at this time of the review. When completed, the research team member will upload the meta-narrative into the patient's protected electronic health via the University of Colorado Hospital secure network.

We will maintain strict data security procedures. All offices and laboratories on the University of Colorado-Anschutz Medical Center have wired and wireless connectivity to institutional networks and are supported by the UC-AMC Information Technologies department. The UC-AMC Information Technologies department

infrastructure staff maintains, updates, and troubleshoots these services in order to provide 24/7 availability. After-hours support is available by pager.

The PI stores all research data on central servers that are managed by the University Information Technology department. Servers and other sensitive equipment are located in secure, climate-controlled server rooms on the UC-AMC. All electronic information systems that contain federal data are protected from unauthorized access by strong password security protocols. Network security is in compliance with University of Colorado Human Subjects Division, HIPAA, and FERPA standards. All electronic information systems that contain federal data are protected from unauthorized access by strong password security protocols. Network security is in compliance with University of Colorado Human Subjects Division, HIPAA, and FERPA standards. Personal computers are networked by either high-capacity wired or secure wireless connections. The potential for breach of confidentiality is being addressed through the maintenance of a secure “log-on” system on the secure computer server dedicated to this project. Interview audiotapes will be transcribed and stored on the secure computer server. It is necessary to collect participant information in order to pay participants for their participation. Identifying information for participants (e.g., name, address, and telephone number) may be required for the telephone contacts made by research staff. This information will be kept in a logbook stored in a computer file that is protected by a secure log-on system; only research team members who require that information will have log-on access to the identifying information. These security precautions will be explained in the consent form.

All data will be stored electronically on password-protected servers, folders and files, and only study staff and the investigators will have access to these study-related electronic files. Weekly assessment data will be entered into separate electronic databases directly by study staff from the paper or phone interview data collection. To obtain the patient’s medical records data, we will create and maintain a separate, password-protected file of a data matching key with the names, medical record numbers, dates of admission, and study ID number for each participant. We will request electronic data for the enrolled participants from the staff who maintain the clinical data bases and match the data to the study ID number. Once all data have been matched and we have a complete set with only study identifiers (names and medical records numbers will be deleted), we will destroy the key linking study identifiers to personal identifiers for the enrolled patients. This will happen no later than the end of the study period.

The digital audio files and transcripts of the qualitative interviews will be reviewed and edited to remove all identifying information (such as names, places, or specific unique details of the patient or nurse). Original recordings and transcript files will be destroyed when the final usable set of transcripts is complete, also no later than the end of the study period.

